9.7.2. Disease Definitions and Ascertainment

Being overweight with at least one weight-related comorbid condition or having obesity at the time of conception is a condition for inclusion into the main analysis cohorts, specifically, for comparison of the tirzepatide exposed cohort with the AOM unexposed comparator cohort. Disease information, including date of diagnosis, height, and weight (used to calculate BMI, where obesity is defined as $BMI \geq 30 \text{ kg/m}^2$ and overweight is defined as $BMI \geq 27 \text{ kg/m}^2$), will be collected at the time of enrollment into the study. History of maternal weight and weight-related comorbid conditions at the time of initial prescribing (if applicable), at the time of conception, at enrollment, during pregnancy, and near the time of delivery will be collected from HCPs.

9.7.3. Outcome Definitions and Ascertainment

Table 9.3 presents the definitions of the outcomes. For outcomes not simply reported by the HCP, additional information on outcome ascertainment is provided.

Table 9.3. Definitions of Outcomes

Outcome	Clinical Definition	Operational definition
Major congenital malformation (MCM)	An abnormality of body structure or function that is present at birth; is of prenatal origin (i.e., birth defect); has significant medical, social, or cosmetic consequences for the affected individual; and typically requires medical intervention ⁴⁸	
The registry defines and codes MCMs with criteria specified by the CDC MACDP (Annex 3).⁴⁹ When participants who reside in Europe are enrolled, MCMs will also be defined and coded using the criteria specified by the EUROCAT⁵⁰ (Annex 3).
 
Exclusion criteria for MCM analyses include exposure to known teratogens and/or investigational medications, and/or congenital infectious agents (e.g. zika, TORCH, HIV). To avoid misattribution of the malformation to the medication, MCMs not known to be associated with medication exposure, such as chromosomal abnormalities, genetic syndromes, fetal alcohol syndrome, prematurity-related conditions in infants born at <36 gestational weeks (e.g., patent ductus arteriosus, patent foramen ovale, inguinal hernias, or undescended testes), and positional effects (e.g., hip dislocation due to breech position or abnormal skull shape due to crowding by multiple fetuses), will not be considered MCMs in the statistical analyses.⁵¹
 
Adjudication process: A panel of 2–3 independent experts in clinical genetics and neonatology, blinded to exposure, will review all malformations reported to the registry among live and non-live births and classify them using the CDC's MACDP system for US-reported cases (and EUROCAT, for EU-reported cases). Additionally, the birth defect evaluators will provide the organ system involved, etiology of the defect (e.g., chromosomal abnormality, prematurity), and approximate timing of the development of observed defects. If additional information is needed to aid in classification, the birth defect evaluators will request additional information using the targeted follow-up process outlined in Section 9.6.2. These assessments will be recorded in the study database. If there is a discrepancy, a third expert will independently review and code the case serving as tie breaker. These reviews will occur soon after the malformation is reported. Additional reviews will occur if new information is received for the case. The SAC that will not be blinded to exposure will assess the possible temporal association between exposure (to tirzepatide) and the development of observed defects. Additionally, the SAC will review all malformation cases reported to the registry and reach consensus on the coding of each case. The sponsor will not be involved in any activities related to case review or adjudication.


Outcome	Clinical Definition	Operational definition
Minor congenital malformation	An anomaly or abnormality of body structure that is present at birth, is of prenatal origin (i.e., birth defect), poses no significant health problem in the neonatal period, and tends to have limited social or cosmetic consequences for the affected individual ⁴⁸	The registry defines and codes minor congenital malformations with criteria specified as defined by the CDC. ⁵² The same process for adjudicating MCMs will be used to adjudicate minor congenital malformations.
Pre-eclampsia	
A disorder of pregnancy associated with new-onset hypertension, which occurs most often after 20 weeks of gestation and frequently near term, and proteinuria. Or, in the absence of proteinuria, it is defined as new-onset hypertension with the new onset of any of the following:
 
 • Thrombocytopenia: platelet count less <100,000/mL • Renal insufficiency: serum creatinine concentrations >1.1mg/dL or a doubling of the serum creatinine concentration in the absence of other renal disease • Impaired liver function: elevated blood concentrations of liver transaminases to twice normal concentration • Pulmonary edema • New-onset headache unresponsive to medication and not accounted for by alternative diagnoses or visual symptoms^{53,54} 	As reported by HCP.
Eclampsia	New-onset tonic-clonic, focal, or multifocal seizures in the absence of other causative conditions such as epilepsy, cerebral arterial ischemia and infarction, intracranial hemorrhage, or drug use ⁵³	As reported by HCP.
Gestational diabetes	Any degree of glucose intolerance with onset or first recognition during pregnancy ⁵⁵	As reported by HCP.

Outcome	Clinical Definition	Operational definition
Pregnancy-induced hypertension	A disorder of pregnancy defined as a systolic blood pressure of 140 mmHg or more or a diastolic blood pressure of 90 mmHg or more, or both, on 2 occasions at least 4 hours apart after 20 weeks gestation, in a woman with a previously normal blood pressure ^{53,56}	As reported by HCP.
Maternal cardiac disease	Maternal cardiac disease will include but will not be limited to heart failure, coronary artery disease, pregnancy-associated myocardial infarction, cardiomyopathy, heart valve disorders	As reported by HCP.
Hyperemesis gravidarum	Uncontrolled vomiting requiring hospitalization, severe dehydration, muscle wasting, electrolyte imbalance, ketonuria, and weight loss of more than 5% of body weight ⁵⁷	As reported by HCP.
Inadequate gestational weight gain	Gestation weight gain that is below the recommended range at term based on pregnancy weight category	The registry will use the 2009 gestational weight gain guidelines of the Institute of Medicine ⁵⁸ to determine inadequate maternal weight gain at term per maternal pre-pregnancy BMI category in singleton and twin gestations.
Spontaneous abortion (SAB)	An involuntary fetal loss or the expulsion of the products of conception occurring at <20 gestational weeks	Section 9.7.5 provides information on the methods used to calculate gestational age.
Stillbirth	As defined by the ACOG, an involuntary fetal loss occurring at ≥ 20 gestational weeks or, if gestational age is unknown, a fetus weighing ≥ 350 g ⁵⁹	Section 9.7.5 provides information on the methods used to calculate gestational age.
Induced abortion	An intervention that is intended to terminate a suspected or known ongoing intrauterine pregnancy and that does not result in a live birth ⁶⁰	As reported by HCP.
Preterm birth	A live birth occurring at <37 gestational weeks	Section 9.7.5 provides information on the methods used to calculate gestational age.

Outcome	Clinical Definition	Operational definition
Small for gestational age (SGA)	Birth weight <10th percentile for sex and gestational age using standard growth charts for full and preterm live-born infants ⁶¹	For the determination of SGA, the registry will utilize the sex-specific international growth reference standards from the INTERGROWTH-21st for those born between 24 ^{0/7} and 42 ^{6/7} gestational weeks. ^{62,63} The INTERGROWTH-21st standards are the latest available global reference standards, representing contemporary information from an international, multi-ethnic, diverse population, and have been specifically developed for modern research.
Large for gestational age (LGA)	Birth weight >90th percentile for sex and gestational age using standard growth charts for full and preterm live born infants ⁶⁴	For the determination of LGA, the registry will utilize the sex-specific international growth reference standards from the INTERGROWTH-21st for those born between 24 ^{0/7} and 42 ^{6/7} gestational weeks. ^{62,63} The INTERGROWTH-21st standards are the latest available global reference standards, representing contemporary information from an international, multi-ethnic, diverse population, and have been specifically developed for modern research.
Rapid weight gain ^{65,66} (RWG) ^a	A positive change in the weight-for-age z-score greater than 0.67 between 2 different ages of childhood ⁶⁷	For the determination of rapid weight gain, the registry will utilize the sex-specific international growth reference standards from the WHO for children ages 0 to 59 months. The WHO growth standards are recommended for use in the US for infants and children 0 to 2 years of age. ⁵⁷
Postnatal growth deficiency ^a	Weight, length, or head circumference in <10 th percentile for sex and age using standard growth charts	Postnatal growth deficiency will be evaluated at 4 and 12 months of infant age; deficiencies in weight, length, and head circumference will be evaluated separately. For the determination of postnatal growth deficiency, the registry will utilize the sex-specific international growth reference standards from the WHO for children ages 0 to 59 months. The WHO growth standards are recommended for use in the US for infants and children 0 to 2 years of age. ⁶⁸
Infant developmental delay ^a	Failure to achieve the developmental milestones for age, as defined by the CDC ⁶⁹	Infant developmental delay will be evaluated at 4 and 12 months of infant age for each CDC-defined category (social/emotional, language/communication, cognitive, and movement/physical development), separately. ^b HCPs will indicate on the data collection forms whether infants are meeting CDC-defined milestones (yes/no) for each category and age. Infants who are failing to achieve at least one milestone in any category will be considered developmentally delayed in that category.

Abbreviations: ACOG = American College of Obstetricians and Gynecologists; CDC = Centers for Disease Control and Prevention; EUROCAT = European Registration of Congenital Anomalies and Twins; HCP = healthcare provider; INTERGROWTH-21st = International Fetal and Newborn Growth Consortium for the 21st Century; LGA = large for gestational age; MACDP = Metropolitan Atlanta Congenital Defects Program; MCM = major congenital malformation; RWG = rapid weight gain; SAB = spontaneous abortion; SAC = Scientific Advisory Committee; SGA = small for gestational age; US = United States; WHO = World Health Organization

^a Infants born preterm or SGA will be excluded from these calculations.

^b Equivalent assessments are also accepted (e.g., Munich Functional Developmental Diagnostic- MFED or Bayley's Scale of Infant Development)

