The exploratory objective is to describe and compare the prevalence of additional maternal, fetal and infant outcomes of interest between pregnant individuals treated with tirzepatide for weight management during pregnancy and the two comparator cohorts of pregnant individuals (AOM active comparator cohort and AOM unexposed comparator cohort). The exploratory outcomes of interest are as follows:

- Hyperemesis gravidarum
- Inadequate gestational weight gain
- Maternal cardiac disease (e.g., heart failure, cardiomyopathies)
- Large-for-gestational age; and
- Infant rapid weight gain

Study design

This is a prospective, observational cohort study designed to evaluate the association between tirzepatide treatment for weight management during pregnancy and subsequent maternal, fetal, and infant outcomes.

Population

The study population will include three cohorts of pregnant individuals:

- Tirzepatide exposed cohort: A cohort of individuals who are treated with tirzepatide for weight management during pregnancy
- Anti-obesity medication (AOM) active comparator cohort: A cohort of individuals who are treated with pharmacotherapy other than tirzepatide or other therapies with GLP-1 RA activity for weight management during pregnancy. The comparator AOMs may include, but not limited to, orlistat, setmelanotide, and naltrexone-bupropion.
- AOM unexposed comparator cohort: A cohort of individuals who have obesity or are overweight with at least one weight-related comorbid condition at the time of conception; and who are not treated with tirzepatide, GLP-1 RA therapies, or any products for weight management during pregnancy.

Variables

Individuals will be considered treated during pregnancy if at least one dose of a product is taken during pregnancy or during the period equal to up to 5 times the product's half-life prior to conception. Based on the half-life of tirzepatide (5 days), individuals will be considered as treated with tirzepatide during pregnancy if a dose is taken within 25 days prior to conception. The primary outcome of MCMs will be adjudicated by independent experts, blinded to exposure, using the CDC's MACDP system or EUROCAT. Secondary and exploratory outcomes will be ascertained by assessment of HCPs who provide care during pregnancy and/or pediatric care.

Covariates of interest will include demographics, risk factors for the study outcomes, comorbidities, concomitant medications, and predictors of treatment with tirzepatide.

Data sources

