9.20. Responsibilities

Sponsor

Eli Lilly and Company, the sponsor, will provide financial support, general oversight, and decision-making for the registry. The sponsor may transfer any or all its study-related responsibilities to a contract research organization and other third parties; however, the sponsor retains overall accountability for these activities.

Principal Investigator/Co-Investigator

The principal investigator/co-investigator is responsible for providing oversight of the registry and all submissions (protocol, amendments) to the IRBs/IECs. The principal investigator/co-investigator may delegate responsibilities for study-related tasks where appropriate to individuals who are sufficiently qualified by education, training, and experience, in accordance with applicable regulations. The principal investigator will be available to the sponsor and the SAC for ongoing consultations regarding the review, analysis, and conduct of the registry.

Virtual Registry Coordination Center (VRCC)

The VRCC is responsible for assisting the principal investigator/co-investigator in all aspects of participant recruitment, informed consent, data collection, and management. As is noted in Section 9.15, the VRCC staff is fully trained on and compliant with SOPs regarding the protection of human subjects and data privacy.

Scientific Advisory Committee

The SAC is responsible for overseeing the scientific affairs of the registry, including its ongoing monitoring. The SAC is an independent (not associated with the Sponsor) group of recognized experts in the fields of teratology, epidemiology, maternal and fetal medicine, and therapeutic areas from academia and private practice. They will meet prior to finalization of each summary report, to review and classify reported MCMs (as described in Section 9.7.3) and to review the accumulated body of data from the registry and to carry out any actions required, including review of recruitment and retention, and review and interpretation of analyses, reports, and publications of registry data. As warranted, the SAC may recommend specific strategies to heighten awareness of the registry. The SAC may meet on ad hoc occasions, if indicated, to address potential signals or other issues that arise during the registry.

The responsibilities of the SAC will be described in a charter to which each SAC member will agree.

10. Management and Reporting of Adverse Events/Adverse Reactions

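### An advisory committee that knows exposure reaches consensus on the coding of every malformation, and the protocol never makes the blinded panel's code final, so blinded classification of the primary outcome is not assured

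*Protocol*

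**What the plan says.** Section 4 (Abstract, Variables) makes the claim without qualification: "The primary outcome of MCMs will be adjudicated by independent experts, blinded to exposure, using the CDC's MACDP system or EUROCAT".

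Table 9.3 in Section 9.7.3 describes two steps.

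- **Blinded panel.** Two or three "independent experts in clinical genetics and neonatology, blinded to exposure, will review all malformations reported to the registry". They assign the classification, organ system, etiology and approximate timing, and their assessments are entered in the study database. Disagreement is closed inside the panel: "If there is a discrepancy, a third expert will independently review and code the case serving as tie breaker".
- **Scientific Advisory Committee (SAC).** "The SAC that will not be blinded to exposure will assess the possible temporal association" between exposure and defect. The next sentence adds that "the SAC will review all malformation cases reported to the registry and reach consensus on the coding of each case".

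Section 9.20 confirms the second role. The SAC meets before each summary report is finalised "to review and classify reported MCMs (as described in Section 9.7.3") and also "to review the accumulated body of data from the registry".

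Table 9.6 in Section 9.11.2.1 counts, as the numerator of the primary analysis, the MCMs that adjudication has confirmed, after removing categories judged not to be drug-related. It does not say whether the panel's or the SAC's code is meant. Table 9.3 applies the same adjudication process to minor malformations, a secondary outcome.

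**The concern.** Coding a malformation is the act that creates the primary outcome. It decides whether a defect is major or minor. It also decides whether a case is removed as chromosomal, genetic, prematurity-related or positional. Published code lists narrow these decisions but leave room for judgement in individual cases.

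If the people making them know who took tirzepatide, misclassification can differ between cohorts. A suspicious coder may keep borderline defects in the exposed cohort; a sceptical one may find a non-drug etiology for them. The relative risk can therefore move either way. Propensity-score weighting does not repair this, because it balances baseline covariates and does nothing about how the outcome is coded. The SAC also sees the accumulating registry data, so it may know the emerging direction of the comparison when it codes.

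**Working it through.** **1. The passages side by side**

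| Question | Blinded panel | SAC |
|---|---|---|
| Knows exposure? | No (Section 9.7.3) | Yes (Section 9.7.3) |
| Which cases? | All | All |
| Produces a code? | Yes, with third-expert tie-break | Yes, by consensus (9.7.3); classifies (9.20) |
| When? | Soon after a case is reported | Before each summary report |
| Stated to be final? | No | No |
| Named as the source for Table 9.6? | No | No |

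The tie-break means the panel can close every case without the SAC, so the SAC's coding is not there to resolve what the panel left open. No passage masks the SAC for coding, limits it to unresolved cases, or bars it from changing the panel's code. Two readings remain. If the SAC's consensus changes nothing, the text gives it no purpose. If it changes the code, the analysed outcome is not a blinded one. The protocol does not choose between them.

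**2. The plan's own sample size (Section 9.9.1)**

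Inputs: comparator prevalence p1 = 0.03, relative risk 3 so p2 = 0.09, 80% power, two-sided 0.05, 1:1, Fisher's exact test with the Walters approximation.

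Power = Φ( √(2n) × [arcsin√(p2 − 1/(2n)) − arcsin√(p1 + 1/(2n))] − 1.960 )

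At n = 265: 23.02 × (0.3014 − 0.1795) − 1.960 = 0.845, and Φ(0.845) = 80.1%. At n = 264 it is 79.9%. The stated 265 is reproduced. Enrolment: 265/0.9³ = 363.5, so 364 per cohort and 3 × 364 = 1,092 in total, as stated.

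**3. How many cases carry the result**

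Expected cases: 265 × 0.03 = 7.95, about 8 in a comparator cohort; 265 × 0.09 = 23.85, about 24 in the tirzepatide cohort under the design alternative.

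Two-sided Fisher test, 265 live births per cohort:

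| Exposed vs comparator cases | p |
|---|---|
| 24 vs 8 (design scenario) | 0.005 |
| 23 vs 8 | 0.009 |
| 24 vs 9 | 0.011 |
| 20 vs 8 | 0.031 |
| 19 vs 8 | 0.046 |
| 18 vs 8 | 0.068 |
| 19 vs 9 | 0.079 |

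From the design scenario, 24 − 18 = 6 exposed cases must be recoded before significance is lost. One case decides the result only when the count already lies at the boundary. In the other direction, starting from equal counts of 8 and 8, 19 − 8 = 11 further exposed cases would have to be counted to reach p < 0.05.

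**4. Effect on power for an assumed share recoded**

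The documents give no recoding rate, so this is an assumed range. If a share s of true exposed cases is recoded out, the observed relative risk is 3(1 − s). The Walters formula with p2 = 0.09(1 − s) and n = 265 gives:

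| s | Observed RR | Power |
|---|---|---|
| 0 | 3.0 | 80% |
| 10% | 2.7 | 68% |
| 20% | 2.4 | 53% |
| 30% | 2.1 | 37% |

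Both tables rest on crude tests. The primary analysis is a weighted regression, so they show scale, not the p-values the study would report.

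**The case against.** The strongest reply is that blinded adjudication does take place. A blinded panel reviews every reported malformation, assigns its etiology, breaks its own ties and leaves a record against which any later recode could be checked. The Abstract and Table 9.6 can both be read as referring to that panel, with the SAC as later oversight. The SAC is independent of the sponsor, the sponsor is kept out of case review, the coding criteria are external, and the excluded categories are listed with examples. The SAC's duties are to be set out in a charter that is not shown, and the statistical analysis plan may name the analysed variable.

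Much of this stands. A reader might infer that the SAC's code replaces the panel's, or that the primary outcome is simply unblinded. The protocol says neither. A reader might also infer that one recoded case would generally reverse the conclusion; the Fisher table shows that this is true only at the boundary.

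Three points do not answer the concern. Independence from the sponsor is not blinding, because knowledge of exposure is what creates the bias. The SAC needs exposure to judge temporality, but coding is a separate task that does not need it. A charter or analysis plan could name the final code, but the protocol itself gives an unblinded body a coding role over every case, and that wording must be reconciled with the Abstract.

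**Conclusion.** The point holds as a gap in the stated adjudication process. Blinded coding comes first, but the protocol then has an unblinded committee reach consensus on the code of each case and never says which code is analysed. Blinded classification of MCMs, and of minor malformations through the shared process, is therefore not assured, and the relative risk could be biased in either direction. That the outcome is in fact unblinded is not established.

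The size cannot be fixed from the documents, since it depends on how often the SAC would depart from the panel and in which cohort. With about 8 comparator cases expected, small numbers of recoded cases matter: six of 24 exposed cases would remove significance in the design scenario, and recoding 10% to 30% of exposed cases (assumed) would cut power from 80% to between 68% and 37%. The ambiguity concerns the primary outcome and is cheap to remove, so it should be settled before malformation cases are coded.

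**What to change.** 1. In Table 9.3 and Table 9.6, state that the blinded panel's locked code, including the third-expert tie-break, is the only classification used in the MCM and minor-malformation analyses.
2. Limit the unblinded SAC to temporality and signal review after that code is locked, with no authority to change it. Alternatively, give the SAC exposure-masked cases for coding and reveal exposure only once its coding is recorded; in that case state how its code relates to the panel's.
3. Send any SAC query about a code back to the blinded panel, and keep an audit trail of the change.
4. Align the Abstract, Section 9.7.3, Section 9.11.2.1, Section 9.20 and the SAC charter.

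The cost is wording in those places and, if the SAC is to code, masking of the case packets. No new staff, data or sample size is needed, and the SAC keeps its temporality assessment.
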